6.2.1. Qualification for the treadmill test

Patients will be qualified for the treadmill test based on the result of an electrocardiographic examination (ECG), and the test on a treadmill will be carried out by authorized investigators under the supervision of the doctor.

6.2.2 The evaluation of the claudication distance

The treadmill test will be carried out according to Gardner protocol (Gardner et al., 1991). Patients will march on a treadmill at a constant speed of 3.2 km/h. The initial angle of inclination will be 0% and will be raised by 2% every 2 minutes (Table 4). When the patient reports pain (i.e., grade 2 on a subjective pain assessment scale), the time of occurrence of the claudication will be recorded, from which the claudication distance will be calculated (DG_{CH}). The test will be interrupted when very severe pain occurs that prevents further walking (step 5 corresponding to maximum walking time), and the maximum walking time will then be recorded. The maximum walking time will be used to estimate the maximum walking distance (DG_{MAX}).

Table 4. Parameters of the treadmill test according to Gardner protocol

Time	Level	Speed [mph]	Speed [kph]	Distance [m]	Slope [%]
00:00	1	2,0	3,2	0	0,0
02:00	2	2,0	3,2	107	2,0
04:00	3	2,0	3,2	213	4,0
06:00	4	2,0	3,2	320	6,0
08:00	5	2,0	3,2	427	8,0
10:00	6	2,0	3,2	533	10,0
12:00	7	2,0	3,2	640	12,0
14:00	8	2,0	3,2	747	14,0
16:00	9	2,0	3,2	853	16,0

Abbreviations: mph- miles/hour; kph-km/hour

6.2.3. Evaluation of exercise tolerance.

Evaluation of exercise tolerance will be carried out based on effort duration and a survey and biochemical exponent.

Based on the duration of the effort, the individual oxygen ceiling value (VO_{2max}) and the energy expenditure expressed as metabolic equivalent MET-s will be estimated. Table 5 gives the MET-s values calculated from the parameters for the cardiological treadmill test, according to Ramped Bruce Protocol; (Ramped Bruce Protocol; Bires AM et al., 2013).

Table 5. Results of the treadmill test depending on the severity of ischemia in the Fountaine scale. Energy expenditure expressed as metabolic equivalent of MET-s is given. The values of MET-s were estimated based on parameters of cardiological treadmill test according to Bruce's ramp protocol.

Time	Level	Speed [mph]	Speed [kph]	Distance [m]	Slope [%]	MET-s	Fountaine scale
00:00	1	2	3,2	0	0,00	2,1	-
00:20				18			I Ib
00:40				36			I Ib
01:00				54			I Ib
01:20				71			I Ib
01:40				89			I Ib
02:00	2	2	3,2	107	2,00	3,2	I Ib
02:20				125			I Ib
02:40				143			I Ib
03:00				161			I Ib
03:20				178			I Ib
03:40				196			I Ib
04:00	3	2	3,2	213	4,00	4,3	I Ia
04:20				231			I Ia
04:40				249			I Ia
05:00				267			I Ia
05:20				284			I Ia
05:40				302			I Ia
06:00	4	2	3,2	320	6,00	5,3	I Ia
06:20				338			I Ia
06:40				356			I Ia
07:00				374			I Ia
07:20				391			I Ia
07:40				409			I Ia
08:00	5	2	3,2	427	8,00	6,4	I Ia
08:20				445			I Ia
08:40				463			I Ia
09:00				481			I Ia
09:20				498			I Ia
09:40				516			I Ia

10:00	6	2	3,2	533	10,00	7,5	Ila
10:20				551			Ila
10:40				569			Ila
11:00				587			Ila
11:20				604			Ila
11:40				622			Ila
12:00	7	2	3,2	640	12,00	8,5	Ila
12:20				658			Ila
12:40				676			Ila
13:00				694			Ila
13:20				711			Ila
13:40				729			Ila
14:00	8	2	3,2	747	14,00	8,5	Ila
14:20				765			Ila
14:40				783			Ila
15:00				801			Ila
15:20				818			Ila
15:40				836			Ila
16:00	9	2	3,2	853	16,00	9,6	Ila

Abbreviations: mph- miles/hour; kph-km/hour; MET-s - metabolic equivalent.

The degree of intensity of fatigue changes after the completed effort will also be assessed using a subjective scale to evaluate the degree of fatigue (Borg scale; Smarż et al. 2015). At rest and 3 minutes after the exercise, the intensity of metabolic exercise acidosis will be assessed based on lactate concentration in capillary blood taken from the fingertip. At the same time, venous blood will also be collected for biochemical and genetic tests.

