Among the planned clinical trials that may establish pleiotropic rivaroxaban actions, the **PRE -FER-AF study** (PREvention of thromboembolic events - European Registry in Atrial Fibrillation) is mentioned as the most important. This study aims to determine the efficacy of oral anticoagulants other than vitamin K antagonists (NOAC) in preventing endothelial dysfunction and atherosclerosis progression **in patients with atrial fibrillation**. Patients with no previous clinically apparent history of CAD, PAD, or stroke will be randomly assigned to the NOAC (dabigatran or rivaroxaban) or placebo-taking group. It is planned to determine vascular endothelial function in long-term therapy after 12 and 24 months. The thickness of the intima-media complex in the carotid arteries will also be measured. This study will assess whether long-term treatment with rivaroxaban brings measurable benefits in relation to the first stages of atherogenesis and atherosclerosis development. **However, it will not provide information on the effect of the drug on the progress of PAD or cardiological capacity of patients.**

3. The objective

The study aims to assess the protective efficacy of rivaroxaban (trade name of the medicinal product Xarelto), administered together with acetylsalicylic acid (ASA), in comparison with the effectiveness of ASA alone, with respect to intermittent claudication and cardiological capacity in patients with PAD over a 3-month period.

4. Type of study

Prospective, observational, unblinded (open), randomized, clinical-control, single-centre.

5. Description of the study group (age, gender, health status, size of the group)

The study will include patients with symptomatic peripheral artery disease (PAD), hospitalized in the The Lord's Transfiguration Clinical Hospital of PUMS, the Department of Vascular, Endovascular, Angiology and Phlebology, monitored in the adjacent Vascular Outpatient Clinic, or referred by cooperating physicians who will use a different protocol of anticoagulation

pharmacotherapy to prevent thrombotic events. The recommended pharmacotherapy does not exceed the standard of treatment in patients with PAD.

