6.2. Treadmill test

The test will be carried out in the Laboratory of Functional Research of the Department of Physiology and Biochemistry of the University of Physical Education in Poznań; in the absence of contraindications. The subjects will be tested at each of the test dates to assess the claudication distance on the Katana S30p medical treadmill (Lode B.V., Netherlands). Before performing the test, patients will undergo an initial, minimum 6-minute implementation of the principles of research, primarily to familiarize them with the way of moving on the treadmill (Mika et al. 2009). Additionally, they will be instructed not to support themselves on treadmill railings during the march. The total time of each test will not exceed 16 minutes 40 seconds, and the regeneration time will be at least 5 minutes.

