6.4. Endpoints of the study

The endpoints of this study and the complications were developed in accordance with the results of the COMPASS study. Parameters related to the results of the treadmill test were added. The study endpoints are summarized in Table 6. The complications related to possible bleeding risk for PAD patients are presented in Table 7.

Table 6. Endpoints of the study

Parametr	Study
Primary outcomes	
Rate of stroke	COMPASS
Rate of myocardial infarction	COMPASS
Rate of cardiovascular death	COMPASS
Rate of death	COMPASS
Prespecified limb outcomes	
Rate of acute limb ischaemia	COMPASS
Rate of major amputation	COMPASS
Rate of all vascular amputations	COMPASS
Treadmill tests outcomes	
Change in the distance of intermittent claudication in the test according to Gardner's protocol (ΔD_{ch} ; ΔD_{max}).	This study
Change in the value of oxygen uptake (ΔVO_{2max})	This study
Change in energy expenditure expressed as the metabolic equivalent of MET-s ($\Delta MET-s$)	This study

Table 7. Safety outcomes for patients with PAD

Parametr	Study
Rate of major bleeding	
Rate of fatal bleeding	COMPASS
Rate of non-fatal symptomatic intracranial haemorrhage	COMPASS
Rate of non-fatal, non-intracranial haemorrhage symptomatic bleeding into a critical organ	COMPASS
Rate of other major bleeding (surgical site bleeding requiring reoperation or bleeding leading to hospitalization)	COMPASS
Rate of fatal or symptomatic bleeding into a critical organ	COMPASS
[Rate of fatal or symptomatic bleeding into a critical organ or surgical site bleeding leading to re-operation]	[COMPASS- not used in this study]
Rate of ISTH major bleeding	COMPASS
Sites of bleeding (frequency of occurrence)	
Gastrointestinal	COMPASS
Intracranial	COMPASS
Genitourinary	COMPASS
Ocular	COMPASS
Skin	COMPASS
Respiratory	COMPASS
Other	COMPASS
Minor bleeding	COMPASS

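### ΔVO2max and ΔMET-s are estimated from the walking time that also gives ΔDMAX, so they cannot support a separate conclusion on cardiological capacity

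*Protocol*

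**What the plan says.** Section 3 of the protocol sets the comparison "with respect to intermittent claudication and cardiological capacity in patients with PAD over a 3-month period", so two targets are named.

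Section 6.2.2 defines the test. Speed is fixed: "Patients will march on a treadmill at a constant speed of 3.2 km/h". The stopping rule is leg pain: "The test will be interrupted when very severe pain occurs that prevents further walking". Distance comes from time: "The maximum walking time will be used to estimate the maximum walking distance". Section 6.2 adds a second way for a test to end: "The total time of each test will not exceed 16 minutes 40 seconds".

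Section 6.2.3 then takes VO2max and MET-s from the same source: "Based on the duration of the effort, the individual oxygen ceiling value" and the MET-s value are estimated, the latter tabulated by test time in Table 5. No equation for VO2max is given. No expired-gas measurement is described; the gasometry in section 6.5.4 is a venous blood test.

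Table 6 in section 6.4 nevertheless gives "Change in the value of oxygen uptake" its own row, and ΔMET-s another, beside the distance row. SAP section 3 tests at P < 0.05, mentions a Bonferroni correction only for genotypes, and does not say how these outcomes relate to each other.

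Section 6.2.3 also collects measures that are not calculated from duration. One is the Borg fatigue score. Another is lactate: "the intensity of metabolic exercise acidosis will be assessed based on lactate concentration in capillary blood taken from the fingertip". Neither appears in Table 6.

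**The concern.** If three outcomes are computed from one stopwatch reading, agreement among them is arithmetic and not corroboration. The label matters too. A patient whose claudication eases walks longer, and the estimated oxygen ceiling rises even if the heart has not changed. The plan has no means of separating the two.

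ΔVO2max and ΔMET-s are the only rows of Table 6 that could carry a statement on cardiological capacity. The others are clinical events, limb events and walking distance. Echocardiography (section 6.1) and the post-test ECG (section 6.2.4) are recorded but are not endpoints. A report that followed the plan could therefore present one walking effect as a separate effect on capacity, and no rule in the SAP prevents it.

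**Working it through.** **Inputs.** Speed 3.2 km/h (section 6.2.2, Table 4); stage times, distances and MET-s (Table 5); cap 16 min 40 s (section 6.2); target difference 5% and example SDs 5.8 and 11.6 (SAP section 2). Assumed, because the documents give no baseline: mean DMAX 300–450 m with SD 120–180 m, and SD of the percentage change 5.8–30.

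**1. Reproduce the plan's distances.** 3200 m ÷ 60 min = 53.33 m/min. At 0, 2, …, 16 min this gives 0, 106.7, 213.3, 320.0, 426.7, 533.3, 640.0, 746.7 and 853.3 m. Tables 4 and 5 print 0, 107, 213, 320, 427, 533, 640, 747 and 853 m, a match within 0.4 m. So DMAX = 53.33 × time.

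**2. MET-s against distance.** Table 5 gives 2.1, 3.2, 4.3, 5.3, 6.4, 7.5, 8.5, 8.5 and 9.6 at those distances. Pearson r = 0.992 and Spearman 0.996 over nine stages; r = 0.9999 over the first seven. The line through those seven is MET-s = 2.125 + 0.534 × minutes. Since 0.534 ÷ 53.33 = 0.0100, ΔMET-s ≈ 0.0100 × ΔDMAX, or about 1.07 MET-s per 107 m. The value 8.5 appears at both 12:00 and 14:00, so the mapping is non-decreasing but not strictly increasing.

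**3. Change scores.** The protocol does not say whether MET-s are interpolated or read as whole stages. Both were simulated (200,000 patients per row, mean change 1%, distances truncated just under the cap):

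| Baseline mean / SD (m) | SD of change (%) | r with ΔDMAX, interpolated | r with ΔDMAX, whole stage | Zero ΔMET-s, whole stage |
|---|---|---|---|---|
| 300 / 120 | 5.8 | 0.994 | 0.483 | 87% |
| 300 / 120 | 11.6 | 0.993 | 0.679 | 74% |
| 300 / 120 | 30 | 0.991 | 0.906 | 46% |
| 450 / 180 | 5.8 | 0.910 | 0.530 | 82% |
| 450 / 180 | 30 | 0.969 | 0.926 | 37% |

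Under whole-stage reading no patient had ΔMET-s opposite in sign to ΔDMAX. Under interpolation this follows from the non-decreasing table. The lower whole-stage correlations are lost resolution, not new information.

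**4. VO2max.** Write the undisclosed estimate as f(t, x), where t is walking time and x any patient characteristics. Then ΔVO2max = f(t₁, x₁) − f(t₀, x₀). Age, sex and weight would hardly change over three months, so x₁ ≈ x₀ and the change follows t. This is reasoning from the description, not a documented formula.

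**5. The cap.** 16 min 40 s = 16.67 min, and 16.67 × 53.33 = 889 m. A patient who reaches it is not stopped by pain, but DMAX and MET-s, and VO2max as described, are then all censored at the same point. The cap adds no independent information.

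**6. Sample size.** The SAP's 30 per group (power 0.9071 at SD 5.8) and 115 per group (0.9023 at SD 11.6) reproduce with the two-sided t-test. They concern walking distance and are unaffected.

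**The case against.** The other side has real points. The protocol states openly that these values come from duration. Section 6.2.3 bases exercise tolerance on a survey and biochemical measures as well. The SAP's null hypothesis concerns claudication distance and effort tolerance, power concerns only ΔDCH and ΔDMAX, and the study calls itself a pilot. The objective does not say which measure is to support cardiological capacity. All of this stands, and it makes the matter one of labelling and interpretation.

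A reader might infer several stronger things that the documents do not support:

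- **That any DMAX effect must appear in all three outcomes.** A 5% change is 0.05 × 300 = 15 m to 0.05 × 450 = 22.5 m at the assumed baselines, well inside a 107 m stage. With whole-stage reading, a DMAX effect could fail to show in MET-s.
- **That VO2max is a known function of time.** Only MET-s has a documented mapping.
- **That every test is pain-limited.** The time cap is a second way to end.
- **That lactate and Borg, adjusted for walking time at the same visit, should take over as the capacity outcomes.** Follow-up walking time is measured after randomisation and is what the drug is meant to change, so adjusting for it would break the randomised comparison. Both measures also follow the same limited walk, and Borg is subjective in an open-label trial.
- **That lactate is certainly available at every test.** Protocol section 6.5.1 gives a total of two venous and two capillary collections during the tests. Section 6.5.2 describes venous sampling twice in each test, and its capillary sentence is incomplete.

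**Conclusion.** The concern holds in this form. DMAX, MET-s and, as described, VO2max rest on one measured quantity, so they supply one independent piece of information on effort, not three. For MET-s this follows from Table 5. For VO2max it assumes that any other inputs to the unstated equation are nearly constant within a patient, which is less secure if follow-up is extended towards the 12 months that section 6.3 allows. The correlations of change scores depend on the assumed baselines and spreads; the shared input does not.

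The consequence is confined to interpretation. As listed, these two outcomes cannot answer the cardiological-capacity half of the objective, while the walking-distance comparison stands. The documents do not show that the investigators intend to count three confirmations; they only leave that reading open.

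**What to change.** In Table 6 and SAP section 3, label ΔVO2max and ΔMET-s as descriptive conversions of DMAX, with no separate hypothesis test and no separate claim. Limit the conclusion drawn under the objective to claudication or walking performance and exercise tolerance.

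If lactate and Borg are reported as supportive exercise-tolerance measures, compare them between arms without adjusting for follow-up walking time. Before planning any change in lactate between visits, reconcile sections 6.5.1 and 6.5.2 on whether blood is taken at every test.

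The core change is wording only and needs no new data. Its cost is a narrower claim: the trial would no longer offer a conclusion on cardiological capacity.

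### Protocol Table 5 gives the same MET-s value at 12% and 14% slope, so changes in MET-s that cross 14 minutes are scored about 1.1 MET too small

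*Protocol*

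**What the plan says.** Protocol section 6.2.2 sets the test: "The treadmill test will be carried out according to Gardner protocol", at a constant 3.2 km/h, starting level and adding 2% slope every 2 minutes. Section 6.2 caps a test at 16 minutes 40 seconds, so levels 8 and 9 can be reached.

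Section 6.2.3 estimates VO2max and MET-s from the duration of effort and points to Table 5 for the MET-s values. The rows that matter are:

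- level 1: "00:00 1 2 3,2 0 0,00 2,1"
- level 6: "10:00 6 2 3,2 533 10,00 7,5"
- level 7: "12:00 7 2 3,2 640 12,00 8,5"
- level 8: "14:00 8 2 3,2 747 14,00 8,5"
- level 9: "16:00 9 2 3,2 853 16,00 9,6"

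The last number in each row is the MET-s value. The 20-second rows in between carry distances but no MET-s. The caption names a different test as the source, the Bruce ramp protocol: "The values of MET-s were estimated based on parameters of cardiological treadmill test according to" that protocol. Neither document gives an equation, a rule for times between levels, or a reason for a plateau.

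Section 6.4, Table 6, lists "Change in energy expenditure expressed as the metabolic equivalent of MET-s" among the treadmill outcomes.

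**The concern.** At fixed speed a steeper slope is more work, so equal energy cost at 12% and 14% needs an explanation, and none is given. The value at 16% equals what the earlier rows would lead one to expect at 14%. This looks like one value entered twice and the rest of the column moved down a row.

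The change in MET-s is a listed outcome, exercise capacity is part of the study objective (section 3), and effort tolerance is part of the SAP's null hypothesis (SAP section 2). An analyst who uses the table as printed would record wrong change scores for some of the better walkers.

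**Working it through.** **Inputs.** All come from protocol Table 5: speed 3.2 km/h; slopes 0, 2, ..., 16%; MET-s 2.1, 3.2, 4.3, 5.3, 6.4, 7.5, 8.5, 8.5, 9.6.

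**1. Are the late rows otherwise sound?** 3.2 km/h is 3200/60 = 53.33 m per minute. 14 × 53.33 = 746.7 m (printed 747) and 16 × 53.33 = 853.3 m (printed 853). The distances reproduce, so the anomaly lies in the MET-s column alone.

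**2. Steps between levels.** 1.1, 1.1, 1.0, 1.1, 1.1, 1.0, then 0.0, then 1.1.

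**3. Reproducing levels 1 to 7.** The protocol gives no formula, so two forms were fitted to the column itself.

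- Closed form, inferred: MET = (3.2/3) × (level + 1).
- Least-squares line through levels 1 to 7: MET = 2.125 + 0.534 × slope%. Residuals for these levels are within 0.04 MET. The line gives 9.60 at 14% and 10.67 at 16%, so the printed values lie 1.10 and 1.07 below it.

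| Level | Time | Slope % | Printed | (3.2/3) × (level + 1) | Printed minus pattern |
|---|---|---|---|---|---|
| 1 | 0:00 | 0 | 2.1 | 2.1 | 0.0 |
| 2 | 2:00 | 2 | 3.2 | 3.2 | 0.0 |
| 3 | 4:00 | 4 | 4.3 | 4.3 | 0.0 |
| 4 | 6:00 | 6 | 5.3 | 5.3 | 0.0 |
| 5 | 8:00 | 8 | 6.4 | 6.4 | 0.0 |
| 6 | 10:00 | 10 | 7.5 | 7.5 | 0.0 |
| 7 | 12:00 | 12 | 8.5 | 8.5 | 0.0 |
| 8 | 14:00 | 14 | 8.5 | 9.6 | -1.1 |
| 9 | 16:00 | 16 | 9.6 | 10.7 | -1.1 |

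Both forms agree to one decimal on the last two rows.

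**4. Effect on change scores if the table is read stepwise.**

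| Change in walking time | Printed table | Pattern continued |
|---|---|---|
| 10 to 14 min | 8.5 - 7.5 = 1.0 | 9.6 - 7.5 = 2.1 |
| 10 to 16 min | 9.6 - 7.5 = 2.1 | 10.7 - 7.5 = 3.2 |
| 12 to 14 min | 8.5 - 8.5 = 0.0 | 9.6 - 8.5 = 1.1 |
| 12 to 16 min | 9.6 - 8.5 = 1.1 | 10.7 - 8.5 = 2.2 |
| 14 to 16 min | 9.6 - 8.5 = 1.1 | 10.7 - 9.6 = 1.1 |

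Every change that crosses 14:00 loses 1.1 MET. The same holds with the sign reversed for a decline. A patient at or beyond 14:00 at both visits has the right change score, because both values are low by the same amount.

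**5. If values are interpolated instead.** The line between 12:00 and 14:00 is flat at 8.5, so any change inside that interval scores zero.

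**6. Effect on an arm's mean (stepwise reading).** Each patient who moves up across 14:00, net of those who move down, lowers the arm's mean change by 1.1/n. With the SAP's 30 per group that is 1.1/30 = 0.04 MET per net patient. How many patients cross is not in the documents.

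**The case against.** The strongest reply is that little depends on this column. MET-s is a treadmill outcome, not one of the event rates that Table 6 lists as primary. The SAP bases power on the changes in claudication and maximum distance, which do not use MET-s. At constant speed, MET-s derived from duration carries the same walking information as maximum distance, which is intact. The same table serves both arms, and only patients who get well past 12 minutes are touched. All of this stands and limits the reach of the error. It does not make the scores right for an outcome that the plan lists and will report.

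Three stronger readings are tempting, and the documents do not support them.

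- A reader might infer that all gains beyond 12 minutes are understated. Under stepwise scoring only changes that cross 14:00 are wrong, and declines shrink as well as gains.
- A reader might infer that the Bruce ramp source causes the understatement. The repeated value causes it. The rows carry Gardner speeds and slopes, and the text does not show whether Bruce readings were copied or a Bruce-related calculation was applied to Gardner stages. Neither size nor direction of a bias can be derived.
- A reader might infer that 2-minute steps hide the SAP's 5% effect. That 5% is a between-group difference in mean percentage change, not a gain made by each patient, and no step rule is stated. Even with steps, if patients are spread evenly within a level, the mean away from 14:00 is preserved. For example, a 20 m gain crosses a level in 20/106.7 = 0.19 of patients, and 0.19 × 1.07 MET = 0.20 MET, the same as continuous scoring.

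It is also fair to say that the row slip is an inference. It fits the numbers exactly, but the protocol does not confirm it.

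**Conclusion.** The point holds in this limited form. Table 5 contradicts its own progression at 14% and 16%, and the two rows are about 1.1 MET low if the pattern of levels 1 to 7 continues. That continuation is the main assumption: 9.6 and 10.7 are not in the documents, and a stated reason for the plateau would change the conclusion. The loss is the whole of a change from 12 to 14 minutes, half of one from 12 to 16, and about half of one from 10 to 14 (1.1 of 2.1).

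It affects the change in MET-s, and VO2max only if that is taken from the same values. The number of patients affected cannot be stated, because the documents give no distribution of walking times. The event rates, the claudication distances and the sample size do not depend on it. The Bruce attribution is a separate question of validity, with no size or direction claimed. The table should be corrected before results are derived, but no primary or powered conclusion is shown to be at risk.

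**What to change.** Before any MET-s result is derived, do one of the following:

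- **Minimum:** recompute the 14% and 16% rows with the calculation used for levels 1 to 7, or state why the value does not rise. Add the rule for times between levels.
- **Preferred:** calculate MET-s for each patient from the Gardner speed, the slope and the recorded stop time, with one equation written into the SAP and applied the same way at both visits and in both arms. If VO2max is derived from the same quantities, use the same equation.

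In either case, reconcile the Bruce ramp attribution in section 6.2.3 with the Gardner stages by saying how the MET-s values were obtained.

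The cost is two cells, or one formula in the data set. No new measurement is needed, because maximum walking time is already recorded under section 6.2.2. The small downside is that any values already calculated from the printed table would change and would have to be redone.
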